#### **6.4.7 Columbia Suicide Severity Rating Scale (C-SSRS)**

The C-SSRS is a brief, Investigator-administered questionnaire that provides for the identification, quantification, and standardized assessment of the occurrences and severity of suicidal ideation and behavior.

The Baseline version of the C-SSRS will be administered to all subjects at the Screening Visit. The “Since Last Visit” version will be used at all subsequent study visits (and Early Termination, if necessary). The Investigator or other designated, qualified individual at the clinical site will perform these assessments.

## **7 ADVERSE EVENTS**

### **7.1 Definition of an Adverse Event**

An AE is defined as “any untoward medical occurrence in a patient or clinical investigation subject administered a pharmaceutical product that does not necessarily have a causal relationship with this treatment.” An AE can therefore be any unfavorable and unintended sign (including an abnormal laboratory finding), symptom, or disease temporally associated with the use of a medicinal (investigational) product, whether or not related to the medicinal (investigational) product. This includes any newly occurring event or previous condition that has increased in severity or frequency since the administration of study drug.

Adverse events will be identified at the times indicated in the schedule by asking the subject a neutral question such as: “How have you been feeling since your last visit?” Adverse events may also be reported spontaneously at any time. Any adverse or unexpected events, signs, or symptoms will be fully recorded on the AE form in the eCRF including details of onset, resolution, frequency, severity (as defined below), seriousness, relationship to the drug, effect on the study drug, treatments administered, and outcome. Any AE that occurs during the study will be followed, whenever possible, until it returns to the baseline condition or becomes stable with no further change expected.

Beginning with the first dose of study drug on Day 2, all AEs occurring up to study completion, must be recorded in the eCRF. All changes in health occurring prior to study drug dosing should be recorded as medical history.

### **7.2 Definition of a Serious Adverse Event (SAE)**

An SAE is any event or reaction that fulfills one or more of the following outcomes:

- Results in death
- Is life threatening. This means that the patient is at risk of death at the time of the event; it does not mean that the event hypothetically might have caused death if it were more severe
- Requires inpatient hospitalization or prolongs an existing hospitalization
- Results in persistent or significant disability or incapacity
- Results in a congenital defect or birth defect
- Is an important medical event that may not be immediately life threatening or result in death or hospitalization but that may jeopardize the patient or require intervention to prevent one of the above outcomes.

Medical and scientific judgment should be exercised in deciding whether a case is serious.

All SAEs must be recorded on the eCRF adverse event form as “serious” and submitted promptly during the study. All SAEs should be monitored until they are resolved or are clearly determined to be due to a subject’s stable or chronic condition or intercurrent illness.

Reports for hospitalization for elective procedures do not need to be reported as SAEs, if there are no precipitating signs/symptoms or worsening of a pre-existing condition that necessitated the procedure. However, SAEs must be reported for any complications resulting from a procedure that prolonged the hospitalization.

Serious adverse events should be reported as outlined in Section [7.5](#).

### **7.3 Collection of Adverse Events**

The collection of AE information will start with the first dose of study drug (Day 2) and continue through the post-withdrawal follow-up phone call (i.e., 7 days after Visit 7). The collection of SAE information will start with the first dose of study drug (Day 2) and continue 30 days after the subject's last dose of study drug. For subjects who terminate early, all AEs and SAEs should be treated as medically appropriate. Should a subject have an ongoing SAE at the last study contact or has an SAE within 30 days after Visit 7, the subject will continue to be followed as specified in Section 7.8.

To detect the occurrence of AEs and SAEs, the physician should use non-direct neutral questioning of the subject at each post-dose clinical visit. Information of AEs and SAEs may also be given voluntarily by the subject at any time during the study.

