#### **4 STUDY POPULATION**

Approximately 312 adult subjects (male or female) with a diagnosis of ADHD per DSM-5™ criteria will be enrolled. Subjects must be 18 to 55 years old, inclusive, at the time of Screening.

Subjects who satisfy the inclusion/exclusion criteria will undergo a 7-day washout of previous ADHD stimulant medications, and AR19 or placebo will then be initiated at 10 mg/day the morning after Visit 2. Depending on treatment group, the daily dose will be increased in 10-mg increments every week to 20 or 40 mg/day. The study duration from first dose of study drug to the follow-up visit is expected to be approximately 6 weeks.

Subjects will be monitored for safety and for therapeutic response to AR19 treatment. Safety and clinical response assessments will be performed at each visit or more frequently if clinically indicated.

Each subject must meet all the inclusion criteria and none of the exclusion criteria to be eligible for enrollment in the study. Waivers to inclusion/exclusion criteria will **NOT** be granted.

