## **5.9 Prior, Concomitant, and Prohibited Medications**

### **5.9.1 Prior Medications**

Subjects who were taking a prescription psychotropic medication other than a stimulant or sedative hypnotic at the time of Screening are not eligible for the study. Subjects who have recently taken prescription psychotropic medications for ADHD (except stimulants or sedative hypnotics) are eligible, if the psychotropic medication will be discontinued at least 28 days prior to the Baseline Visit. Any non-study ADHD stimulant medication must be discontinued at least 7 days prior to the Baseline Visit 2. Subjects must not have participated in any other clinical study in which an investigational drug was administered within 60 days of the Screening Visit and must not participate in other investigational trials during this study.

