### **6.1.1 Screening Visit – Study Visit 1 (Day -30 to -1)**

Before any study-specific procedures are performed, the subject must receive an explanation of all study procedures and must sign and date an Institutional Review Board (IRB)-approved written informed consent form. A subject ID number will be assigned at the Screening Visit (Visit 1), for any subject who signs an ICF.

The timing of the Screening Visit must take into account planned absences at the clinical site and the timing of the study visits according to the Schedule of Events [Table 6.1.1](#).

The Screening Visit may be split into more than one calendar day if needed, if all required assessments are performed within 30 days of Baseline (Visit 2).

Diagnosis of ADHD based on DSM-5™ criteria and the CAADID will be confirmed for all subjects at entry by a physician or mental health profession (Master's level or higher), having at least five years of experience using ADHD rating scales for assessment of ADHD and also using the DSM for assessment of psychiatric disorders. A MINI-7.0.2 will be administered on all subjects to assist in screening for other mental health disorders that may be exclusionary.

Following confirmation of appropriate age at the Screening Visit, a diagnosis of ADHD consistent with DSM-5™ criteria will be confirmed prior to the evaluation of other inclusion and exclusion criteria.

During the Screening Period, the following activities will be performed:

- Obtain subject informed consent
- Review of inclusion/exclusion criteria
- Review of medical history
- Review of medication history (ADHD stimulant medication should be discontinued 7 days prior to the Baseline Visit)
- Demographics
- Completion of the following diagnostic criteria for ADHD performed by a physician or mental health professional (Master's Level or higher) with the required experience as outlined above:
  - CAADID
  - DSM-5™ Diagnoses
- Mini International Neuropsychiatric Interview (MINI) 7.0.2
- AISRS
- CGI-S
- C-SSRS Baseline Visit version
- Height, body weight, and body mass index (BMI)
- Blood pressure and pulse (in triplicate via automated machine), respiratory rate, and temperature
- Resting 12-lead ECG
- Physical examination
- Laboratory tests (see [Appendix A](#))

- Serum chemistry panel (including serum pregnancy test for females of child-bearing potential)
- Hematology
- Urinalysis
- Urine drug screen for drugs of abuse testing (performed at the site)
- Blood alcohol level
- HbA1c

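### SAE collection starts only at the first dose, so a serious event between consent and Day 2, including one during a stimulant washout required by the protocol, needs no SAE form or 24-hour report

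*Protocol*

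**What the plan says.** Protocol 7.3 sets the window for serious events. It opens at the first dose: "The collection of SAE information will start with the first dose of study drug (Day 2". It closes late, since collection is to "continue 30 days after the subject's last dose of study drug". Non-serious events have the same opening date. Protocol 7.1 says where earlier events go: "All changes in health occurring prior to study drug dosing should be recorded as medical history".

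Consent comes well before that. Protocol 6.1.1 requires it before any study-specific procedure, at a Screening Visit between Day -30 and Day -1. The first dose is on the morning of Day 2 (Protocol 6.1.2).

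Treatment is withdrawn in between. Protocol 4 says that eligible subjects "will undergo a 7-day washout of previous ADHD stimulant medications", and Protocol 5.9.1 makes this a requirement: "Any non-study ADHD stimulant medication must be discontinued at least 7 days prior to the Baseline Visit 2". Exclusion criterion 19 (Protocol 4.2) tolerates a positive urine drug result at Screening when it is due to current ADHD stimulant therapy, so a subject may give consent while still taking a stimulant.

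**The concern.** Some subjects stop a working treatment because the protocol asks them to, after they have signed consent. If one of them is then hospitalized or has another serious event before Day 2, the protocol directs the site to record a medical-history item. It does not require an SAE form, a seriousness criterion, a causality judgment or a 24-hour report.

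Timely knowledge of harm from taking part in the study, as distinct from harm from AR19, is at stake. SAP 11 plans no official data monitoring, so individual SAE reports are the main prompt route to the sponsor and, through Protocol 7.5.2, to the IRBs.

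The gap matters most for subjects who leave before randomization. A serious washout event may itself make a subject ineligible, for example through the suicidality criterion (exclusion 23) or an abnormal finding at Baseline (exclusion 14).

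**Working it through.** No sample size, power or alpha figure bears on this point. The check compares sections and counts days.

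**1. Length of the uncovered interval.** Inputs: Screening runs from Day -30 to Day -1 (Protocol Table 6.1.1), Baseline is Day 1, and the first dose is on Day 2. The schedule shows no Day 0.
- Longest: 30 + 1 = 31 calendar days.
- Shortest the schedule permits (Screening on Day -1): 1 + 1 = 2 days.
- Shortest for a subject still on a stimulant at consent, who needs 7 days off drug before Baseline: 7 + 1 = 8 days.

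**2. How much of the washout falls in it.** Let d be the number of days by which the stimulant was stopped before consent. Of the 7 required days off drug, max(0, 7 - d) fall after consent.
- d = 0 (still on drug at consent): 7 days, the whole washout.
- d = 3: 4 days.
- d of 7 or more, or no prior stimulant: 0 days.

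The documents do not say how many subjects fall in each group.

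**3. Whether another section closes the gap.**
- *Schedules:* the adverse-event row is blank at Screening and Baseline in both Protocol Table 6.1.1 and SAP 14.1.
- *Protocol 6.4:* AEs are assessed at post-dose visits. Section 3.2.2 refers to each visit, but 7.3 and both schedules give the operative timing.
- *Protocol 7.5.1:* the 24-hour rule is expressly extended to events after treatment ends. It says nothing about events before treatment starts.
- *SAP 8.4:* treatment-emergent events begin at first dose. The SAP adds no pre-dose SAE collection.

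None of these closes it.

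**4. Where such an event could appear.**
- *Subject later dosed:* medical history is reviewed at Visit 2, then coded and summarized on the Safety Population (SAP 5.3). Suicidal ideation or behavior would appear in the Visit 2 C-SSRS, which SAP 8.9 summarizes by visit. Neither entry carries the seriousness and relatedness ratings of Protocol 7.4.3 or leads to expedited reporting.
- *Subject never randomized:* enrollment occurs at randomization (Protocol 5.4), disposition counts enrolled subjects (SAP 4.2), and the Safety Population needs randomization and a dose (SAP 4.1.1). No planned summary table would hold the event.

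**The case against.** The strongest reply is that this is a coherent design choice. Protocol 7.1 defines an AE by reference to administration of a product, an event before the first dose cannot be due to AR19, and the start date is applied consistently. That stands as far as AR19's own safety profile goes: randomized comparisons do not change. It does not answer the point about harm from a withdrawal or procedure that the protocol requires.

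Three stronger readings are tempting, and the documents do not support them.

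- *A reader might infer that such events are never reported and that the sponsor cannot see them.* The SAE definition in Protocol 7.2 carries no start date, and subjects may volunteer information at any time (7.3), so a site might report one. Visit 2 medical history goes into the eCRF, which the monitor checks against source (8.2.1). Protocol 10.1 asks investigators to give the IRB necessary safety updates. SAP 3 lists all study data by subject, and the SAE listing in SAP 8.4 is not confined to treatment-emergent events. The supportable statement is that reporting is not required.
- *A reader might infer that every prior stimulant user has the whole washout in the gap.* Protocol 5.9.1 fixes only how long before Baseline the drug must be stopped. A subject who stopped before consent has part or none of it there.
- *A reader might express the gap as a share of participation.* The share depends on the end point chosen. At the longest screening it is 31/(30 + 36) = 47% up to Visit 7. Up to 30 days after a last dose on about Day 36 it is 31/(30 + 36 + 30) = 32%. Both are ceilings, and neither measures risk.

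It is also fair to object that an earlier start date alone would not be enough. Protocol 7.4.2 rates relatedness to study drug only, so a washout event would have no suitable causality category.

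**Conclusion.** The concern holds as a gap in required safety reporting. Between signed consent and the Day 2 dose, for up to 31 days, Protocol 7.1 and 7.3 require no SAE form and no 24-hour report. The whole 7-day washout falls in that interval for subjects still on a stimulant at consent, and part or none of it for the others. The consequence is clearest for subjects never randomized. In dosed subjects the event may be recorded, but it is not rated or expedited.

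This rests on reading 7.1 and 7.3 as the operative instructions where 7.2 gives no start date. If a site reads 7.2 as overriding them, its instructions conflict and the wording still needs repair. The day count assumes no Day 0.

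The documents give no event rate, so no number of missed events can be estimated. The primary analysis, its alpha and power, and the treatment-emergent comparisons are unaffected. The case for change is that it is cheap and improves safety oversight.

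**What to change.** - **Protocol 7.1 and 7.3:** start SAE collection and 24-hour reporting at signature of the consent form, at least for events possibly related to washout or a study procedure. Keep non-serious AE collection from the first dose. Except these SAEs from the rule that sends earlier events to medical history alone, and word the AE definition in 7.1 to admit them.
- **Protocol 7.4.2:** for pre-dose SAEs, add an assessment of relatedness to washout or to a study procedure.
- **Protocol Table 6.1.1 and SAP 14.1:** mark SAE review at Visits 1 and 2.
- **SAP 8.4:** add a separate listing of pre-dose SAEs, including those in subjects not randomized, and keep them out of the treatment-emergent tables so that comparisons between arms do not change.

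The cost is an amendment to the wording, an added causality item on the existing SAE form, one listing, and some extra SAE reports from screening. The documents do not allow the number of extra reports to be estimated.

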### **7.4 Assessment of Adverse Events**

The Investigator will assess each AE according to severity and relatedness to study drug.

#### **7.4.1 Assessment of Adverse Event Severity**

The following guidelines for rating severity of AEs should be used:

**Mild:** Awareness of signs or symptoms, but easily tolerated; are of minor irritant type; no loss of time from normal activities; symptoms would not require medication or a medical evaluation; signs and symptoms may be transient, disappearing during continued treatment with study medication.

**Moderate:** Discomfort enough to cause interference with usual activities; the study medication may have been interrupted.

**Severe:** Incapacitating with inability to do work or do usual activities; signs and symptoms may be of systemic nature or require medical evaluation; the study drug may have been stopped, and treatment for the event may be required.

The term "severe" is often used to describe the intensity of a specific event, as in mild, moderate, or severe myocardial infarction; the event itself, however, may be of relatively minor medical significance, such as severe headache. This is not the same as serious, which is based on subject/event outcome or action criteria usually associated with events that pose a threat to a subject's life or functioning. The Investigator must decide whether each AE meets the definition of an SAE.

#### **7.4.2 Assessment of Adverse Event Relatedness**

The relatedness of an AE to study medication will be determined by the Investigator using the following definitions:

**Related:** The AE is clearly related to the study drug. This assessment means there is evidence to suggest a clear, causal relationship between the study drug and the AE.

**Possibly Related:** The AE may be related to study drug. A “possibly” assessment suggests that the association of the AE with the study medication is unknown; however, the AE is not reasonably supported by other conditions.

**Unlikely Related:** The AE is doubtfully related to study drug. An “unlikely” assessment suggests other conditions, including chronic illness, progression or expression of the disease state, or reaction to concomitant medication, appear more likely to explain the reported AE.

**Not Related:** The AE is clearly not related to the study drug.

#### **7.4.3 Recording of AEs and SAEs**

All AEs occurring during this clinical study will be recorded in the eCRF in precise medical terms, along with the date of onset and the date of resolution. To avoid vague, ambiguous, or colloquial expressions, the AE should be recorded in standard medical terminology rather than the subject's own words. Whenever possible, the Investigator should group signs and symptoms together into a single term that constitutes a single diagnosis. Each AE is to be evaluated for duration, severity, seriousness, and relatedness to the study medication. The severity of the AE and its relationship to the study medication will be assessed by the Investigator.

The action taken and the outcome must also be recorded. The possible actions concerning study medication are:

- Drug withdrawn
- Dose not changed
- Unknown
- Not applicable
- Dose interrupted

Recorded outcomes include:

- Recovered/Resolved
- Recovering/Resolving
- Not recovered/Not resolved
- Resolved with sequelae
- Fatal
- Unknown

## 7.5 Reporting of Serious Adverse Events

### 7.5.1 Serious Adverse Event Notification

Serious adverse events must be reported within 24 hours of knowledge of the occurrence. This includes events that occur following completion of treatment with study drug. Additionally, if an Investigator learns of any SAEs that occurred after study completion for which there is a reasonable possibility of study drug relationship, that event should be reported to the Sponsor within 24 hours.

The eCRF SAE Reporting Form will be completed with as much information as is available and must include information below within 24 hours of when the investigative site becomes aware of the event.

Required SAE information:

- Name of Reporter/Investigator
- Subject identification
- Adverse event term
- Date of onset
- Criteria of seriousness
- Study drug relationship

For assistance regarding SAE reporting, please contact the [REDACTED]  
[REDACTED]

### 7.5.2 SAE Expedited Reporting

For each SAE, the Investigator should assess whether there is a reasonable possibility that the event may have been caused by the study drug ("drug related") using the categories given in Section 7.4.2. The Sponsor or designee will notify all Investigators of an SAE. Those SAEs that meet reporting criteria will be submitted to the appropriate Regulatory Authorities as required by clinical trial regulations. The Investigator is responsible for notifying his/her respective IRB.

## 7.6 Procedures for Reporting Pregnancy Exposure and Birth Events

Should a female subject become pregnant or be suspected of being pregnant while participating in this study, the event must be reported to [REDACTED] upon receipt of information by the study staff. While the pregnancy itself is not considered to be an AE or SAE, any pregnancy complications should be recorded as AEs or SAEs (if applicable). Pregnancy must be reported within 24 hours from first knowledge on the pregnancy eCRF. Any pregnancy will be followed through delivery for the observation of any SAEs including congenital abnormalities. Fatalities and spontaneous abortions must be reported as SAEs.

## **7.7 Emergency Unblinding**

Unblinding should occur only when knowing the treatment assignment has a bearing on the medical treatment or evaluation of a subject. Whenever possible, the need to unblind should be discussed with the Medical Monitor prior to unblinding. In the event of an emergency, the Investigator, Pharmacist, or designated qualified individual may obtain the subject's blinded treatment via IWRS. If an individual designated to perform emergency unblinding does not have access to the IWRS, Sponsor Designee may be contacted and can perform the unblinding for that individual. A subsequent written report, including all pertinent details, must be submitted to the Medical Monitor within 24 hours of the unblinding. Whenever possible, the blind of the subject should be maintained.

## **7.8 Follow-up of AEs and SAEs**

All AEs must be followed until they resolve (return to normal or baseline values), stabilize, or are judged by the Investigator to be no longer clinically significant. Serious adverse events observed during the study should be followed by the responsible Investigator at the clinical site until they resolve or stabilize, the subject is lost to follow-up, or the events are otherwise explained.

